8.3.1.1 Modified MDA

Subjects are classified as in modified MDA when they meet the criteria PASI ≤ 1 or BSA ≤ 3 and 4 of the following criteria: TJC ≤ 1, SJC ≤ 1, PtAAP ≤ 15, PGADA ≤ 20, HAQ-DI ≤ 0.5 or tender enthesial points ≤ 1. The difference between the MDA and the modified MDA is that the PASI/BSA criteria is a mandatory criteria.

8.3.2 Disease Activity Score-28 joint count C-reactive protein (DAS28[CRP])

The components for DAS28(CRP) include the TJC and SJC based on 28 joints, hs-CRP (mg/L), and the PGADA (mm). DAS28(CRP) is calculated as follows:

$$DAS28(CRP) = 0.56 * \sqrt{TJC} + 0.28 * \sqrt{SJC} + 0.014 * PGADA + 0.36 * \ln(hsCRP + 1) + 0.96 \quad (12)$$

The hs-CRP values below the limit of quantification should be set to half the limit of quantification for the calculations. The limit of quantification for hs-CRP is 0.16 mg/L.

8.3.3 Bath Ankylosing Spondylitis Disease Activity Index (BASDAI)

The BASDAI is the most commonly used instrument to measure the disease activity of ankylosing spondylitis. The BASDAI is a validated self-reported instrument which consists of 6 NRSs, each with 10 units to measure the severity of the 5 major symptoms: fatigue, spinal pain, peripheral joint pain and swelling, enthesitis, and morning stiffness (both severity and duration) over the last week. The BASDAI questionnaire is available in the Appendix Section 12.6. To give each symptom equal weighting, the average of the 2 scores relating to morning stiffness is taken. The resulting 0 to 50 sum score is divided by 5 to give a final BASDAI score between 0 and 10, with lower scores indicating lower disease activity.

The BASDAI is calculated as follows:

$$BASDAI = \frac{Q1 + Q2 + Q3 + Q4 + \left(\frac{Q5 + Q6}{2}\right)}{5} \quad (13)$$

where Q1 – Q6 are the six question from the BASDAI questionnaire.

If 1 of the 2 morning stiffness measurements (ie, questions: [REDACTED] and [REDACTED]) is missing, the other one will be used for the morning stiffness calculation.

If 1 major symptom of the BASDAI is missing, the sum score of the remaining symptoms will be divided by the number of symptoms assessed. If more than 1 major symptom is missing, the sum score will be set to missing.

8.3.4 Modified Nail Psoriasis Severity Index (mNAPSI)

Subjects with psoriatic nail disease will have a target nail selected at the Baseline visit for evaluation using the mNAPSI. The nail selected should be the most affected nail observed at Baseline and should be the only one assessed throughout the study. The target nail will be scored (0 to 3) for onycholysis/oil drop dyschromia, nail plate crumbling, and pitting and will be scored (0 for “no” or 1 for “yes”) for leukonychia, nail bed hyperkeratosis, splinter haemorrhages and red spots in the lunula. The score for an individual nail ranges from 0 to 13 with higher scores indicative of more severe nail disease. Subjects with nail disease at Baseline are defined as those with a mNAPSI score >0 at Baseline.

If 1 or 2 response items scored on the 0 to 1 scale are missing, the missing response(s) will be imputed by the average of the available responses. Otherwise, the total mNAPSI score will be set to missing.

8.3.6 Leeds Dactylitis Index (LDI)

Dactylitis, the swelling of an entire digit related to articular and periarticular inflammation, is a characteristic of inflammatory spondyloarthropathies, including PsA. Presence of dactylitis will be assessed using the LDI basic which evaluates for a $\geq 10\%$ difference in the circumference of the digit compared to the opposite digit (Healy and Helliwell, 2007; Helliwell et al, 2005). The percent difference between circumferences will be multiplied by a tenderness score (0 for non-tender, 1 for tender). The digits involved and the matching contralateral digit will also be recorded at the same visits. The results from each digit with dactylitis will then be summed to produce a final score.

The following is a table of normative values, which will be used to provide the comparison, if matching digits are thought to be involved ([Table 8–5](#)).

Table 8–5: Normative values for LDI

	Digit	Men	Women
Hand	Thumb	70	58

Table 8–5: Normative values for LDI

	Digit	Men	Women
	Index	63	54
	Middle	63	54
	Ring	59	50
	Little	52	44
Foot	Great toe	82	72
	Second	52	46
	Middle	50	44
	Fourth	50	44
	Little	52	45

The following rules will be applied for the LDI calculation in case of unclear data. If both digits of a given pair are recorded as affected, then each digit will be compared to the normative value. If both comparisons result in a difference greater than 10%, then both digits will contribute to the LDI score. If the circumference of the affected digit is smaller than the unaffected digit, then the LDI will be calculated by comparing the smaller digit to the normative value. If a digit is recorded as affected and the circumference of the contralateral digit is missing, the normative value will be used for comparison with the affected digit.

If the LDI CRF page is left empty at Baseline, it will be assumed that no digits were affected. At post-Baseline visits, when LDI cannot be determined, last observation carried forward (LOCF) imputation should be applied.

8.3.7 Psoriatic Arthritis Impact of Disease-9 (PsAID-9)

The PsAID-9 is a patient-reported outcome measure for assessing the impact of PsA in 9 physical and psychological domains, including pain, fatigue, skin problems, work and/or leisure activities, functional capacity, discomfort, sleep disturbance, coping, and anxiety/fear/uncertainty. The questionnaire is available in the Appendix [Section 12.8](#).

Each domain is assessed with a single question using a 0 to 10 NRS. Each domain score is multiplied by a weighting factor and the results are then summed to provide the total score.

$$\begin{aligned}
 PsAID = & Pain * 0.174 + Fatigue * 0.131 + Skin * 0.121 \\
 & + Work\ and/or\ Leisure\ Activities * 0.110 + Function \\
 & * 0.107 + Discomfort * 0.098 + Sleep * 0.089 + Coping \\
 & * 0.087 + Anxiety * 0.085
 \end{aligned}
 \tag{14}$$

The total score ranges from 0 to 10, with higher scores indicating a worse status. A score below 4 out of 10 is considered a patient-acceptable status. A change of 3 or more points is considered relevant absolute change.

If one of the 9 domains is missing, the missing value is imputed using the mean value of the 8 other (non-missing) domains. The imputed value will be used to calculate the PsAID with the formula above. If 2 or more of the domains are missing, the PsAID will be treated as missing.

8.3.8 Psoriatic Arthritis Quality of Life (PsAQoL)

The use of the PsAQoL is recommended by the health regulatory authorities as one of the disease specific Health-Related Quality of Life (HRQoL) measures in PsA (CHMP/EWP/438/04). The questionnaire is available in [Section 12.9](#). The PsAQoL comprises 20 items (0 for “not true” or 1 for “true”) so that the score ranges from 0 to 20 with higher scores indicating worse HRQoL.

If 6 or less item responses are missing, the missing responses will be imputed with the mean of available responses to calculate a total score. If more than 6 items responses are missing, the total score will be left missing.

8.3.9 Short Form – 36 Items Health Survey

The SF-36 measures the following 8 health domains as rated by the subjects over the past four weeks: Physical Functioning, role Physical, Bodily Pain, General Health, Vitality, Social Functioning, Role Emotional, and Mental Health. The questionnaire is available in [Section 12.10](#) and the classification of the questionnaire items to the health domains is shown in [Section 12.11](#).

The SF-36 PCS and MCS are used to measure the two broad components, or aspects, of health: physical and mental. PCS and MCS are based on the aggregate of 8 health concepts described above and all of the eight health domain scales are used to score both components summary measures.

One additional item asks respondents about health change over the past year.

The SF-36 will be calculated using QualityMetric’s Health Outcomes™ Scoring Software 4.5. The software uses updates 2009 U.S. population norms and applies a Full Missing Score Estimation method as follows:

- A health domain score (except the physical functioning domain) will be estimated provided that at least one non-missing response is available within that domain.
- For the physical functioning domain item response theory will be used to develop a model for estimates of the missing score.
- Regression methods are then applied to estimate the PCS and the MCS on the basis of the available domains.

8.3.10 Hospital Anxiety and Depression Scale (HADS)

The HADS was chosen for its well-established psychometric properties and its use in clinical research on biological therapy in subjects with chronic plaque psoriasis (Langley et al, 2010; Dauden et al, 2009). The HADS scores for anxiety and for depression range from 0 to 21 with higher scores indicating worse state. A score below 8 is considered to be normal whereas a score of 15 and above is considered severe (Snaith and Zigmond, 1994).

8.3.11 C-reactive protein (CRP) and high-sensitivity C-reactive protein (CRP)

Blood will be collected for measurement of CRP and hs-CRP. CRP and hs-CRP are indicators for inflammation and are measured in the blood. Hs-CRP is a component of composite efficacy variables, and in addition is also summarized and analyzed as individual variables. For hs-CRP the summary statistics should contain n, geometric mean, geometric CV, median, first and third quartile (Q1 and Q3), minimum, and maximum, where the geometric CV (%) is calculated using:

$$CV = \sqrt{e^{SD_{ln}^2} - 1} \quad (15)$$

with SD_{ln} – the standard deviation of the ln-transformed hs-CRP values.

For descriptive statistics, the observed values and ratio to Baseline values will be displayed.

hs-CRP and CRP values below the limit of quantification should be set to half the limit of quantification for the calculations. The limit of quantification for hs-CRP is 0.16 mg/L and 0.4 mg/dL = 4.00 mg/L for CRP.

8.4 Subgroup analysis

Subgroup analyses will be performed on the primary and secondary efficacy variables. The variables for subgroup analyses are defined in [Section 4.8](#).

Subjects will be counted to have a positive treatment-emergent AbAb status in case the first AbAb positivity occurred up to Visit 7 (Week 12). The definition of first AbAb occurrence is described in [Section 9.2](#).

The derivation of time since first diagnosis of PsA is described in [Section 6.2](#).

All subgroup analyses are based on imputed data and will be summarized using descriptive statistics only.

9 PHARMACOKINETICS AND PHARMACODYNAMICS

9.1 Pharmacokinetics

Bimekizumab plasma concentrations will be summarized for each treatment at each scheduled visit using the PK-PPS, and using a subset of the DBS which includes subjects that belong to both analysis sets, the DBS and the PK-PPS.

If bimekizumab plasma concentration measurements are deemed to be below the level of quantification (BLQ), then for calculation of the derived statistics this sample result will be set to half the lower limit of quantification (LLOQ). The subjects with at least 1 result that is defined as BLQ will also be listed within the respective analysis table. Descriptive statistics will be calculated if at least 2/3 of the values are above the LLOQ. If this is not the case, only median, minimum, and maximum will be presented.

In addition geometric mean bimekizumab plasma concentration time curves will be plotted by treatment group.

The bimekizumab concentrations will also be listed.

9.2 Pharmacodynamics and Immunogenicity

The biomarker data will be separated between LGC assays, multiplex proinflammatory cytokine and chemokine analysis, flow cytometry - TBNK panel, and flow cytometry - Th1/Th2/Th17/Th22 panel. Biomarker variables will be summarized and listed for each treatment at each scheduled visit using the PD-PPS, and using a subset of the DBS which includes subjects that belong to both analysis sets, the DBS and the PK-PPS.

In addition to the PD variables, whole blood will be stored to isolate deoxyribonucleic acid which may be used to examine genetic and epigenetic changes. The blood samples for genetic and epigenetic, and genomic, proteomic/metabolomics will not be analyzed in the interim or final analysis. Variables will be analyzed in a separate analysis as ad-hoc analysis.

The AbAb status will be determined for each visit where samples are taken for drug concentration measures. A cut point will be determined by the bioanalytical laboratory and will be used to determine the AbAb status as “above the cut point” (ACP) or “below the cut point” (BCP). For any AbAb levels that are ACP, a further confirmatory assay will be performed, the results of which will be determined as either “confirmed positive” (CP) or “not confirmed positive” (NCP). For samples that are CP, a further titre assay will be performed and the AbAb titre will be reported.

At each visit:

- Samples that are either BCP or ACP and NCP are defined as AbAb-
- Samples that are ACP and CP are defined as AbAb+

In addition, overall AbAb status should be determined:

- Subject AbAb positivity is defined as having with AbAb+ at any time in the treatment period. This does not include Baseline/pre-treatment
- Subject AbAb negativity is defined with AbAb- at any time in the treatment period. This does also include AbAb+ at Baseline/pre-treatment
- If there is AbAb+ at Baseline/pre-treatment and there is a 4-fold increase in titre at least at one visit during the treatment period, then the subject has also an overall AbAb positivity status.

The visit of the first occurrence of AbAb positivity is defined as the visit when a subject is AbAb+ for the first time during treatment period excluding Baseline/pre-treatment. If there is AbAb+ at Baseline/pre-treatment and there is a 4-fold increase in titre at least at one visit during the treatment period, then the subject’s first occurrence visit is the Baseline Visit.

The number and percentage of subjects with AbAb levels above the specified cut point will be summarized.

In addition, the time point of the first occurrence of AbAb positivity during the Double-Blind Period, and the entire treatment period (excluding Baseline and pre-treatment) will be summarized for each treatment group.

All individual subject-level AbAb results will be listed including the screening assay, confirmatory assay, and titres if applicable. Note, that titre results will only be available, if the confirmatory assay is positive.

Immunogenicity data will be summarized and listed using the PK-PPS analysis set.

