4.8 Examination of subgroups

The following variables for subgroup analyses will be used:

- Age (<45 years, ≥ 45 to <65 years, ≥ 65 years)
- Gender (male, female)
- Geographic region (North America, Europe)
- BASDAI (<4 [mild disease]; ≥ 4 to ≤ 7 [moderate disease]; > 7 to ≤ 10 [severe disease])
- Prior TNF inhibitor exposure (yes, no)
- Treatment-emergent AbAb status (positive, negative)

- Extent of psoriasis involvement (<3%, ≥3% to <10%, ≥10%)
- hs-CRP level (≤ upper limit normal, > upper limit normal)
- Time since first diagnosis of PsA (< 2 years, ≥ 2 years)
- Body weight (<100 kg, ≥100 kg)

Subjects will be counted to have a positive treatment-emergent AbAb status in case the first AbAb positivity occurred up to Visit 7 (Week 12). The definition of first AbAb occurrence is described in [Section 9.2](#).

The derivation of time since first diagnosis of PsA is described in [Section 6.2](#).

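### SAP 9.2: the 4-fold titre criterion never changes overall antibody status, and a Baseline-positive subject with an unchanged titre is counted as treatment-emergent

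*SAP*

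**What the plan says.** SAP 9.2 classifies a sample as AbAb+ when it is above the cut point and confirmed positive, and as AbAb- otherwise. A titre is determined only for confirmed-positive samples. Three bullets then set overall status:

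- Bullet 1: "Subject AbAb positivity is defined as having with AbAb+ at any time in the treatment period", with the rider "This does not include Baseline/pre-treatment".
- Bullet 2: "Subject AbAb negativity is defined with AbAb- at any time in the treatment period", with the rider "This does also include AbAb+ at Baseline/pre-treatment".
- Bullet 3: "If there is AbAb+ at Baseline/pre-treatment and there is a 4-fold increase in titre at least at one visit during the treatment period". Such a person is counted as positive as well.

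A separate paragraph dates the first occurrence of positivity. It is the first AbAb+ visit in the treatment period, leaving out Baseline and pre-treatment. The exception is a Baseline-positive subject with a 4-fold rise, whose first occurrence is set to the Baseline Visit.

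SAP 4.8 takes its subgroup flag from that date ("Subjects will be counted to have a positive treatment-emergent AbAb status in case the first AbAb positivity occurred up to Visit 7 (Week 12"). SAP 8.4 repeats the rule and refers back to 9.2 for first occurrence. SAP 9.2 summarises first occurrence by treatment group for the Double-Blind Period and for the entire treatment period, excluding Baseline and pre-treatment. SAP 10.2 adds a table of TEAEs by timing of onset relative to AbAb status.

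**The concern.** A 4-fold threshold for Baseline-positive subjects has one purpose: to separate antibody that the drug induced or boosted from reactivity that was already there. As the rules are written it does not do this. Overall positivity carries no titre condition, and neither does the general first-occurrence rule. Antibody that merely persists is then reported as arising on treatment.

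Immunogenicity is a secondary objective (SAP 2.1.2). Mixing pre-existing with induced antibody overstates the induced rate. It also blurs any relation between induced antibody and ACR or PASI response in the subgroup tables. The wording of negativity leaves the programmer to decide what a subject with mixed samples should be called.

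**Working it through.** The plan gives no figure here to reproduce. The check is one of logic, followed by a count.

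**Step 1: redundancy.** Let P be at least one on-treatment AbAb+ sample (bullet 1). Let F be Baseline AbAb+ with a 4-fold rise at one or more treatment visits (bullet 3). F needs a titre at a treatment visit. A titre exists only for a confirmed-positive sample, and that sample is AbAb+. So F implies P, and (P or F) equals P.

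**Step 2: overlap.** Let N be at least one on-treatment AbAb- sample (bullet 2 as worded). Any subject with both kinds of sample satisfies P and N.

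**Step 3: dating.** If F holds, first occurrence is Baseline; otherwise it is the first on-treatment AbAb+ visit. The subgroup flag is positive if that visit is no later than Week 12. Five profiles show the result:

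| Baseline | On-treatment samples | Overall status | First occurrence | Treatment-emergent by Week 12 |
|---|---|---|---|---|
| AbAb+ | same titre at every visit | positive | Week 4 | yes |
| AbAb- | AbAb+ at Week 8 only | positive and negative | Week 8 | yes |
| AbAb+ | AbAb- to Week 24, 4x at Week 36 | positive and negative | Baseline | yes |
| AbAb+ | AbAb- to Week 24, 1x at Week 36 | positive and negative | Week 36 | no |
| AbAb+ | AbAb- throughout | negative | none | no |

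The first row is the main error. The third shows that a rise seen only at Week 36 makes a subject treatment-emergent by Week 12. A Baseline date also conflicts with a first-occurrence summary that leaves Baseline out.

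**Step 4: count.** Take six of the AbAb sampling visits in Protocol 8.3 and 8.4 (Weeks 4, 8, 12, 16, 24, 36) and four states per visit: AbAb-, or a titre of 1x, 2x or 4x Baseline. That gives 4^6 = 4,096 profiles per Baseline status. Among Baseline-positive profiles:

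- 4-fold rise met: 4^6 - 3^6 = 4,096 - 729 = 3,367. Overall status changes because of it: 0.
- Overall positive without a 4-fold rise: 3^6 - 1 = 728. Of these, first positive by Week 12: 3^6 - 3^3 = 729 - 27 = 702, all flagged treatment-emergent.
- First-occurrence visit moved by the criterion: 3,367. Week 12 flag flipped by it (AbAb- at the first three visits, 4x later): 4^3 - 3^3 = 64 - 27 = 37.
- Positive and negative at once: 4^6 - 3^6 - 1 = 3,366. The same number holds for Baseline-negative profiles.

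These are logically possible profiles, not expected subjects. Other choices of visits change the counts but not the zero.

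**Step 5: an exclusive rule.** Define positive as Baseline AbAb- with any on-treatment AbAb+ sample, or Baseline AbAb+ with at least a 4-fold rise, and all others as not. Then 728 Baseline-positive profiles move out of the positive class, no Baseline-negative profile changes, and no profile is both.

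**Step 6: size.** Baseline AbAb prevalence is not in the documents. Assuming 2% to 10% of 200 randomised subjects: 200 x 0.02 = 4 and 200 x 0.10 = 20.

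**The case against.** **A more charitable reading of bullet 1.** Its rider may mean that Baseline-positive subjects, not just Baseline samples, are left out. Taken with the rider on bullet 2, such subjects would be negative unless boosted, and bullet 3 would then have a function. The text allows this but does not say it. It also does not rescue the subgroup. The first-occurrence paragraph carries no Baseline condition, so an unboosted constant-titre subject would be negative overall and still treatment-emergent positive at Week 4.

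**The 4-fold criterion is not idle everywhere.** A reader might infer that it has no effect at all. The documents do not support that: it sets first occurrence to the Baseline Visit and can change the Week 12 flag. Only overall status is untouched.

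**The overlap is probably loose drafting.** The negativity bullet most likely means AbAb- at all times. A reader might infer that subjects could appear in both levels of the AbAb subgroup. They cannot, because SAP 4.8 defines that subgroup by first positivity alone. Nor does the SAP say that the TEAE table uses overall status.

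**Placebo samples.** Samples at Weeks 4, 8 and 12 in placebo subjects precede any bimekizumab, because they are drawn before dosing. A reader might infer that they inflate a bimekizumab rate. The documents do not show this. AbAb is summarised by treatment group, SAP Table 12-3 gives it a Placebo column and no All BKZ column, and SAP 10.2.2 already starts placebo subjects' exposure for incidence rates at first bimekizumab. What remains is that SAP 9.2 has no matching rule for AbAb over the entire treatment period.

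**Limited consequence.** Subgroup results are descriptive only (SAP 8.4). All assay results and titres are listed by subject, so boosted and unboosted cases could be separated by hand. This stands, and it bounds the importance of the point.

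**Conclusion.** The rules are wrong as written, on a contained part of the analysis. The redundancy of the 4-fold criterion for overall status follows from bullet 1 read literally together with the titre rule. The mislabelling of unchanged pre-existing antibody as treatment-emergent holds on either reading of bullet 1.

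The outputs at risk are the immunogenicity summaries, the descriptive AbAb subgroup and possibly the TEAE table by onset relative to AbAb status. No hypothesis test is affected, and neither is the primary analysis.

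The 4 to 20 subjects are an upper bound under an assumed prevalence, not an estimate. The bound supposes that every Baseline-positive subject is mislabelled. It counts all 200 randomised subjects, including about 40 on placebo, whereas immunogenicity is summarised on the PK-PPS, which may be smaller.

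**What to change.** Amend the three bullets, the first-occurrence paragraph, and SAP 4.8 and 8.4 together. Changing the bullets alone would leave the subgroup error in place, because the subgroup rests on first occurrence.

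- Treatment-emergent positive: Baseline AbAb- with at least one on-treatment AbAb+ sample, or Baseline AbAb+ with at least a 4-fold on-treatment titre rise.
- Not treatment-emergent: all other subjects. Show Baseline AbAb+ without a 4-fold rise as its own row. The rest are negative, worded as AbAb- at all on-treatment samples.
- First occurrence: the first visit at which the treatment-emergent definition is met. Set the Week 12 subgroup flag from that visit.
- Placebo-randomised subjects, in entire-treatment-period summaries by bimekizumab treatment: count samples only after the first bimekizumab dose, with the Week 12 pre-dose sample as AbAb Baseline.

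The cost is SAP wording and derivation code, with no new samples. The reported positive rate may come out slightly lower.

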3.2.2 Study Periods

The following study periods are defined for the classification by study period:

- Pre-treatment period (Screening period): up to 28 days, ends with the visit date of the first dose of study medication (Visit 2)
- Double-Blind treatment period: starts with the visit date of the first dose of study medication (Visit 2), ends at Week 12 visit date
- Dose-Blind treatment period: starts at the Week 12 visit, ends at Week 48 visit.
- Post-treatment period: the post-treatment period (Follow-up period) is the period after the Week 48 visit

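### SAP Section 9.2 backdates first antibody positivity to Baseline on a later 4-fold titre rise, so titres taken after Week 12 can set the Week 12 antibody subgroup

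*SAP*

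**What the plan says.** **Overall status (SAP Section 9.2).** Three conditions are given.
- Positive: "Subject AbAb positivity is defined as having with AbAb+ at any time in the treatment period", with Baseline not counted.
- Negative: "Subject AbAb negativity is defined with AbAb- at any time in the treatment period".
- If the subject is AbAb+ at Baseline and the titre rises 4-fold at one or more treatment-period visits, "then the subject has also an overall AbAb positivity status".

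**Date of first occurrence (SAP Section 9.2).** The general sentence uses the visit when the subject is "AbAb+ for the first time during treatment period excluding Baseline/pre-treatment". The next sentence overrides it: with AbAb+ at Baseline and a 4-fold rise at any treatment-period visit, the subject's "first occurrence visit is the Baseline Visit". The same section then plans a summary of the time of first occurrence, for the Double-Blind Period and for the entire treatment period, with Baseline and pre-treatment left out. It also notes that "titre results will only be available, if the confirmatory assay is positive".

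**Use of the date (SAP Sections 4.8 and 8.4).** A subject is treatment-emergent positive if first positivity falls at or before Visit 7 (Week 12), with the date taken from Section 9.2. There is no lower bound. This is a subgroup variable for the primary and secondary efficacy variables.

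**Period (SAP Section 3.2.2).** "Dose-Blind treatment period: starts at the Week 12 visit, ends at Week 48 visit".

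**The concern.** A subgroup for a Week 12 response should be fixed by data available at Week 12. Here a titre measured months later can move a subject into the positive group, because the override replaces the date of the later visit with one that always passes the Week 12 cut.

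For subjects randomized to placebo or 16mg, any titre after Week 12 follows the switch to 160mg or 320mg. A placebo subject's Week 12 response could then be tabulated as antibody-positive because of bimekizumab first given after that response was measured.

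There is also a direct inconsistency. A subject dated to Baseline cannot be shown in a first-occurrence summary that excludes Baseline. This touches every Baseline-positive subject with a 4-fold rise, whenever the rise occurs.

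**Working it through.** There is no stated figure to reproduce. The check is to apply the rules as written.

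**Inputs**
- Antibody sampling visits after Baseline (Protocol Sections 8.3.3 to 8.4.9): Weeks 4, 8 and 12 (3 visits), then Weeks 16, 20, 24, 36 and 48 (5 visits). On dosing days blood is drawn before the dose (Protocol Section 11), so the Week 12 sample precedes the switch.
- Section 9.2 also says "The AbAb status will be determined for each visit where samples are taken for drug concentration measures". That would add Weeks 1 and 2, where the protocol lists concentration samples only. These come before Week 12 and do not alter the argument.
- Subgroup rule: positive if first occurrence is at or before Week 12.
- Illustrative titres (an assumption; only the ratio matters): 10 at Baseline, then 20 (2-fold) or 40 (4-fold).

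**Application.** Take a subject with exactly one AbAb+ sample after Baseline and vary its visit.

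| Subject | Only AbAb+ visit at Week 4, 8 or 12 | Only AbAb+ visit at Week 16, 20, 24, 36 or 48 |
|---|---|---|
| Baseline negative | dated to that visit; positive | dated to that visit; not positive |
| Baseline positive, titre 20 | dated to that visit; positive | dated to that visit; not positive |
| Baseline positive, titre 40 | dated Baseline; positive | **dated Baseline; positive** |

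The bottom-right cell is the defect. The two Baseline-positive subjects have the same record through Week 12 and differ only in a later titre. Since a titre exists only for a confirmed-positive sample, neither had any post-Baseline titre by Week 12.

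The label also depends on the data cut. If the only rise is at Week 36, the subject is not positive on data to Week 12 and is positive on data to Week 48.

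**Who is affected.** A Baseline-positive subject with a late 4-fold rise who was AbAb+ at any on-treatment visit through Week 12 is already positive by Week 12 under the general dating sentence. The override changes the Week 12 label only for a subject who is (1) AbAb+ at Baseline, (2) AbAb- at every visit through Week 12, and (3) at or above four times the Baseline titre later.

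**Does any subject need the override to have a date?** No. A 4-fold rise can be seen only at an AbAb+ visit, and the general sentence already dates that subject.

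**The case against.** **The window is not explicit.** Section 9.2 says only treatment period in the dating rule. Section 3.2.2 defines two such periods, and elsewhere the SAP often adds entire, complete or overall when it means the whole span. One could read the rise as limited to the Double-Blind Period when the Week 12 subgroup is built, and the problem would vanish. The Week 48 reading is therefore an inference, but the more natural one. Sections 4.8 and 8.4 point to Section 9.2 without naming a window, and their Week 12 limit has work to do only if first occurrence can fall later.

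**A Baseline date might mark pre-existing antibody.** Then every Baseline-positive subject should receive it, not only those with a 4-fold rise, and it would sit badly with a subgroup labelled treatment-emergent.

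**The practical weight is small.** This stands. Antibody status is one of ten subgroup variables, the subgroup outputs are descriptive only (Section 8.4), and individual screening, confirmatory and titre results are listed, so an affected subject can be found.

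**Stronger readings to resist.** A reader might infer that every Baseline-positive subject with a late rise is misplaced, on the ground that a 4-fold rise was meant to be required of them. The third status condition invites this: it adds nobody, since a rise needs an AbAb+ sample that already meets the first condition. But the first condition makes no exception for Baseline-positive subjects, so the documents do not support it. Nor can a share of subjects be inferred, because no Baseline prevalence or boosting rate is given.

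**Conclusion.** The point holds and is minor. As written, post-endpoint titres can decide the Week 12 antibody subgroup, and the Baseline date contradicts the summary in the same section that excludes Baseline. The subgroup defect rests on reading the treatment period to Week 48; the contradiction does not.

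The number affected may be zero. A reader might infer a threat to the primary result, but the dose-response test and the pairwise comparisons do not use antibody status.

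It should not be said that the effect stops at the subgroup and immunogenicity tables. Section 10.2 plans TEAEs by timing of onset relative to AbAb status, with exposure-adjusted rates. The SAP does not say whether that timing uses the Section 9.2 date; if it does, that table is affected too.

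**What to change.** In Section 9.2, delete the sentence that assigns the Baseline Visit, or replace it so that first occurrence is the on-treatment visit where the positivity condition is first met. This repairs both the subgroup and the timing summary.

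At minimum, let only rises at visits up to Visit 7 count for the subgroup in Sections 4.8 and 8.4. That cures the use of later data but leaves the contradiction with the timing summary.

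In the same edit, change the negativity definition from any time to all times. As worded, a subject with both AbAb+ and AbAb- samples on treatment meets both definitions. This is probably a slip and does not feed the Week 12 subgroup.

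The cost is one sentence, one phrase and a derivation update, with no new samples or assays. Overall positivity is unchanged by the dating edit. In the timing summary, Baseline-positive subjects with a 4-fold rise move from Baseline to their first AbAb+ visit on treatment. A line in Section 10.2 naming the date used for the TEAE table would settle that open question.
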